#### 9.6. Data management

Routine procedures will include checking electronic files, maintaining security and data confidentiality, following analysis plans, and performing quality control (QC) checks of all programmes. Data management will be conducted at the research centre(s) according to internal (e.g. HealthVerity) standard operating procedures (SOPs) or guidance documents.

Security processes will be in place to ensure the safety of all systems and data. Every effort will be made to ensure that data are kept secure so that they cannot be accessed by anyone except select study staff.

Appropriate data storage and archiving procedures will be followed. Standard procedures will be in place to restore files in the event of a hardware or software failure.

#### 9.7. Data analysis

### 9.7.1. Included patients

The number of individuals selected for the study will be reported by treatment group, including the following parameters: attrition of individuals due to study exclusion criteria, the number of eligible individuals included in the study cohort, and the number of individuals excluded for not meeting each inclusion criterion along with the reasons for exclusion. The number of eligible Time 0s and unique individuals will be reported.

Counts and percentages of the reasons for censoring will also be reported.

### 9.7.2. Descriptive analyses

To better understand finerenone treatment patterns, the distribution of baseline finerenone dosage will be described in the treatment group by eGFR and serum potassium levels.

Distributions of the covariates will be described by treatment group. For binary and categorical variables, the frequency distributions (e.g., counts, proportions) will be displayed. For continuous variables, means, standard deviations, medians, first quartiles, third quartiles, first percentile, and 99th percentile will be calculated as appropriate. The relative balance of characteristics across treatment groups (finerenone users vs. comparators) will be described with absolute standardised differences [52] to observe differences in the distribution of characteristics by treatment group. These descriptive analyses will be performed in the crude overall study cohort.

To account for potential confounding resulting from differences in the baseline characteristics of the treatment groups, propensity score methods will be used. Propensity scores will be estimated for each treated and untreated Time 0 using logistic regression with prespecified baseline characteristics as independent variables and finerenone initiation as the dependent variable [53]. After estimation of the propensity scores, the coefficients of the logistic model will be evaluated to understand the relationships between observed covariates and finerenone initiation. The distribution of propensity scores will be plotted by treatment group and assessed. If imbalance of the propensity score distributions is observed (suggesting potential non-exchangeability of the treatment groups), additional steps to improve exchangeability will be considered (e.g., re-evaluation of propensity score variables to ensure that instrumental variables are not included [54], alteration of eligibility criteria to more fully align the treatment groups [55]).

The propensity scores will be used to estimate stabilised inverse probability of treatment (sIPT) weights. Additional propensity score–based weighting techniques may be considered (e.g., average treatment effect in the treated [ATT] weights), as appropriate, based on the observed distribution of propensity scores [53]. The weights will be applied to all analyses, creating weighted pseudopopulations with balanced covariates across treatment groups. Absolute standardised mean differences will also be assessed in the treatment groups after applying the propensity score weights. If residual imbalances of measured characteristics are observed (i.e., absolute standardised differences far from 0) after weighting (suggesting residual confounding), additional refinement of the propensity score approach will be considered (e.g., inclusion of additional covariates, addition of interaction terms or higher-order terms, trimming or truncation of extreme weights, use of ATT weights instead of sIPT weights [56]).

### 9.7.3. Primary effectiveness analyses

The primary composite cardiovascular outcome will be evaluated in an analytic subset after the application of outcome-specific exclusion criteria to ensure analysis of new-onset disease (Section 9.3.3.1) using an outcome-specific propensity score model; the assessment of weighted covariate balance (Section 9.7.2) in this analytic subset will be evaluated.

To account for baseline confounding, the propensity score–based weights will be applied to the cohort to balance characteristics across treatment groups, and analyses will be performed in the weighted cohort [57]. Because the 2 treatment groups will be subject to censoring after follow-up begins, selection bias may be introduced if individuals are censored differentially between treatment groups. To account for this potential bias, time period–specific inverse probability of censoring (IPC) weights will be estimated with logistic regression with censoring status as the dependent variable and updated time-varying characteristics as the independent variables. A full description of included variables and operationalisations will be provided in the SAP. The IPC weights will also be applied to the analysis [57]; the product of the baseline sIPT and time period–specific IPC weights will be applied during each time period of follow-up to account for both baseline confounding and selection bias in follow-up.

The incidence rates and 95% CIs of the composite cardiovascular outcome across all of follow-up will be estimated in the weighted cohort. A weighted cumulative incidence plot will be generated by treatment group using the cumulative incidence function estimator to visualise the occurrence of outcome events by follow-up time, accounting for censoring criteria and the competing risk of death [58]. This approach will estimate the "total effect" of finerenone on the outcome events or the cause-specific cumulative incidence [59]. Time since Time 0 (i.e., treatment initiation) will be the time scale.

As a summary of the relative difference in outcome incidence between the treatment groups, a HR and 95% CI will be estimated with weighted Cox proportional hazards ratios. The 95% CI will be estimated with robust sandwich estimators to account for the sIPT and IPC weighting and for the possibility of a single individual contributing multiple observations with different Time 0s.

To evaluate potentially changing differences over time since treatment initiation, time-specific RRs will be estimated from the cumulative incidence curves by dividing the weighted daily risk estimate for the finerenone group by the daily risk estimate for the comparator group. Similarly, time-specific risk differences will be estimated by subtracting the daily risk estimate for the comparator group from the daily risk estimate for the finerenone group. Time-specific estimates will be calculated at 6 months, 12 months, and 18 months. The 95% CIs for the time-specific RRs and risk differences will be estimated with nonparametric bootstrapping [60].

Before the primary analyses of the efficacy outcomes are performed, a negative control outcome analysis will be performed to evaluate the potential for unmeasured confounding (Section 9.7.7.1).

### 9.7.4. Secondary outcome analyses

#### 9.7.4.1. Individual components of the composite cardiovascular outcome

For the separate secondary analyses of AMI and hospitalisation for heart failure, the same analysis set as that for the primary composite cardiovascular outcome will be used, with the same propensity score model. Each of the 2 outcomes will be evaluated separately; thus, follow-up may differ for the 2 outcomes. For each outcome, the weighted treatment group–

specific incidence rates, cumulative incidence plots, and overall HR will be estimated following the same methods as those for the primary outcome (Section 9.7.3).

### 9.7.4.2. New-onset heart failure

The analyses of new-onset heart failure will be performed in an analysis set after the application of outcome-specific exclusion criteria (Section 9.3.3.2.3). The treatment group–specific incidence rates, cumulative incidence plots, and overall HR will be estimated following the same methods as those used for the primary outcome (Section 9.7.3).

### 9.7.4.3. Change in UACR

The analysis of change in UACR outcomes will be performed in an analysis set restricted to those with baseline UACR values (Section 9.3.3.2.4). Time to a 30% decline in UACR from baseline will be described in each treatment group with incidence rates and cumulative incidence plots. Time to additional thresholds (e.g., 50%, 70%) may also be evaluated separately. Comparisons of the treatment groups using HRs and 95% CIs may be considered, if feasible; to inform the feasibility of performing comparative analyses, the frequency of UACR testing in each treatment group will be described and evaluated for comparability (to be described in the SAP).

### 9.7.4.4. Hyperkalaemia

The analysis of hyperkalaemia will be estimated in the overall study population without any outcome-specific exclusion criteria (Section 9.3.3.2.5). Treatment group–specific incidence rates will be estimated following the same methods as those for the primary outcome (Section 9.7.3).

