Study size	Sample size estimates suggest that there would be a greater than 80% probability of the 95% confidence interval of the relative risks to exclude 1 at total sample sizes of approximately 30,000 individuals (2,727 finerenone users, and the rest comparators) for the higher estimate of composite cardiovascular outcome incidence and 60,000 individuals (5,455 finerenone users) for the lower estimate of composite cardiovascular outcome incidence. For secondary effectiveness and safety outcomes with lower expected incidence, larger sample sizes would be required to achieve the same level of precision.
Data analysis	The characteristics of treated and untreated groups will be described. Incidence rates of outcomes by treatment group will be estimated, and the cumulative incidence over time will be plotted. Outcome occurrence in the treatment groups will be compared with the stabilised inverse probability of treatment-weighted hazard ratios and 95% confidence intervals. Time-specific risk ratios and risk differences will be estimated to describe potentially changing risk over time. Subgroup analyses will be performed, and sensitivity analyses and negative control outcomes will evaluate the impact of potential biases. A secondary objective evaluating a different treatment strategy of finerenone initiation and label-directed uptitration will also be evaluated.
Milestones	The data collection (i.e., start of data extraction for the secondary use of data) is expected to start 01 October 2024 and end 30 June 2025, with the final report of study results expected by 31 December 2025.

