### 8.2. Secondary objectives

The secondary objectives in this study are the following:

• To estimate the risk of the individual components of a composite cardiovascular outcome (i.e., first occurrence of fatal or nonfatal acute myocardial infarction; first

occurrence of hospitalisation for heart failure) in patients with CKD and T2D initiating finerenone compared with that in patients with CKD and T2D not using finerenone (in the same primary study cohort as the primary analysis).

- To estimate the risk of new-onset heart failure in patients with CKD and T2D initiating finerenone compared with that in patients with CKD and T2D not using finerenone (in a subset of the primary study cohort from which patients with a history of heart failure are excluded).
- To estimate the risk of a decline in UACR (i.e., first occurrence of specific UACR decline thresholds) in patients with CKD and T2D initiating finerenone compared with that in patients with CKD and T2D not using finerenone (in a subset of the cohort of patients with baseline UACR values).
- To assess the safety of finerenone by estimating the risk of hyperkalaemia in patients with CKD and T2D initiating finerenone compared with that in patients with CKD and T2D not using finerenone.
- To estimate the risk of the above mentioned outcomes in clinically relevant subgroups of patients with CKD and T2D initiating finerenone compared with that in patients with CKD and T2D not using finerenone.
- To assess the effectiveness of initiating finerenone and titrating dosage according to the approved label by estimating the risk of outcomes of interest in patients with CKD and T2D initiating finerenone and uptitrating to 20 mg (when recommended) compared with that in patients with CKD and T2D not using finerenone.

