  - Atherosclerosis
  - Atrial fibrillation
  - Cerebrovascular disease (stroke or transient ischaemic attack)
  - Congestive heart failure
  - Hypercholesterolaemia
  - Hyperlipidemia
  - Hypertension
  - Peripheral vascular disease
  - Unstable angina
- Other components of the Charlson Comorbidity Index or similar comorbidity score [48,49] (as single entities, not listed elsewhere)
  - Anaemia
  - Chronic obstructive pulmonary disease
  - Congestive heart failure
  - Dementia

- Human immunodeficiency virus
- Liver disease
- Malignancy other than kidney cancer or nonmelanoma skin cancer
- Paralysis
- Other comorbidities
  - Coronavirus disease 2019 (COVID-19) diagnosis
  - Hyperkalaemia (history of hyperkalaemia, more than 90 days before Time 0)
  - Osteoporosis
  - Pneumonia

The following lifestyle cardiovascular factors will be defined, as available in the data:

- Body mass index or evidence of obesity
- Smoking status
- Alcohol abuse

The following healthcare utilisation measures will be identified in the 365 days before and including Time 0 to characterise patients' healthcare access, healthcare-seeking behaviour, and indicators of disease state at the time of index medication initiation:

- Healthcare utilisation
  - Hospital visits and hospital admissions
  - Emergency department visits
  - Long-term care or skilled nursing facility residence
  - Number of eGFR laboratory tests performed
  - Number of serum potassium laboratory tests performed
- Preventive health services
  - Influenza vaccination
  - Pneumococcal vaccination
  - COVID-19 vaccination
  - Bone mineral density test
  - Screening mammogram
  - Other cancer screening
- Frailty indicators [50]
  - Arthritis
  - Bladder dysfunction
  - Dementia
  - Psychiatric illness
  - Weakness
  - Vertigo

The following comedications will be identified in the 183 days before and including Time 0 to characterise individuals' recent treatments and indicators of disease state at the time of index medication initiation:

- Medications for T2D
  - Alpha glucosidase inhibitors
  - Dipeptidyl peptidase-4 inhibitors (DPP-4i)
  - GLP-1 RA
  - Meglitinides
  - Metformin
  - SGLT2i
  - Sulfonamides
  - Sulfonylureas
  - Thiazolidinediones
  - Insulin
- Cardiovascular medications
  - Angiotensin-converting enzyme inhibitors/angiotensin receptor blockers (ACEi/ARBs)
  - Aldosterone receptor blockers
  - Angiotensin receptor-neprilysin inhibitor
  - Anticoagulants

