#### 9.7.6. Subgroup analyses

To evaluate whether the association of finerenone with outcomes of interest differs by clinically relevant subgroups, HRs and 95% CIs across all of follow-up will be estimated in the following subgroups, if feasible due to observed case counts:

- Age groups
- Sex
- SGLT2i use at Time 0
- ACEi/ARB use at Time 0
- GLP-1 RA use at Time 0
- Insulin use at Time 0
- Potassium-sparing diuretic use at Time 0 (for hyperkalaemia only)
- UACR level at Time 0
- eGFR stage at Time 0
- Previous AMI at Time 0 (for AMI only)

As noted, some subgroup analyses will be performed specifically for only select, relevant outcomes.

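### Hyperkalaemia: the covariate list omits baseline serum potassium, and section 9.7.4.4 names no between-group measure although the objective is comparative

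*Protocol*

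**What the plan says.** The secondary objective in Protocol 8.2 is comparative: "To assess the safety of finerenone by estimating the risk of hyperkalaemia in patients with CKD and T2D initiating finerenone compared with that" in patients not using finerenone. Section 9.7.4.4 analyses the overall study population and promises, for each treatment group, that "incidence rates will be estimated following the same methods as those for the primary outcome (Section 9.7.3"). It names no other output.

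The neighbouring sections say more. For the components of the composite, 9.7.4.1 adds "cumulative incidence plots, and overall HR will be estimated following the same methods as those for the primary outcome". For new-onset heart failure, 9.7.4.2 lists "incidence rates, cumulative incidence plots, and overall HR will be estimated following the same methods as those used for the primary outcome". The abstract says in general terms: "Outcome occurrence in the treatment groups will be compared with the stabilised inverse probability of treatment-weighted hazard ratios and 95% confidence intervals". Section 9.7.6 states that "HRs and 95% CIs across all of follow-up will be estimated in the following subgroups" and includes potassium-sparing diuretic use as a subgroup reserved for hyperkalaemia.

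On confounding, 9.3.4 opens by saying that the covariates include risk factors for hyperkalaemia. The potassium-related entries are a history of hyperkalaemia more than 90 days before Time 0, "Number of serum potassium laboratory tests performed", and drugs that affect potassium. The baseline potassium value is not listed. It is used in two other places: 9.2.1.2 excludes a recorded result above 5.0 mEq/L in the 90 days up to Time 0, and 9.7.2 says that "the distribution of baseline finerenone dosage will be described in the treatment group by eGFR and serum potassium levels".

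**The concern.** Current serum potassium plausibly affects both whether a clinician starts finerenone and whether the patient later has hyperkalaemia. The protocol's own text treats it this way. Section 9.2.1.2 makes it an eligibility variable. Section 9.9 explains that excluding recent hyperkalaemia avoids comparing treated patients with untreated ones who are unlikely to be treated and at higher risk. Section 9.3.2.3 shows that potassium below the 5.0 mEq/L cut-off (above 4.8) still bears on how finerenone is used. A variable of this kind belongs in the propensity model for this outcome.

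The second issue is that the section governing the safety analysis, read alone, stops at one rate per group. The overall safety contrast, its effect measure and its interval are not named where the analyst will look for them. Leaving that choice until results are visible is avoidable.

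**Working it through.** The protocol gives no numerical figure for hyperkalaemia, so there is none to reproduce. The check is mainly a comparison of sections.

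**1. Is potassium covered under another name?** Section 9.3.4 lists, as items related to potassium: past hyperkalaemia (more than 90 days back), the number of potassium tests, CKD stage, ACEi/ARBs, other MRAs, potassium-sparing diuretics and potassium binders. None of these is the current value. Where the list wants a laboratory result it says so: HbA1c is entered as the latest value within 183 days. The section leaves definitions and code lists to the SAP, but the list itself is given in the protocol.

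**2. What does the exclusion remove?** Recorded results above 5.0 mEq/L, and hyperkalaemia diagnoses, in the 90 days up to Time 0. No measurement is required. Differences at or below 5.0 mEq/L, and patients with no recent result, remain.

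**3. Would the planned diagnostics reveal an imbalance?** Sections 9.7.2 and 9.7.3 assess balance on the covariates, and refinement is triggered by residual imbalance in measured characteristics. A variable outside the list would not trigger it. The candidate negative controls in 9.7.7.1 (asthma visits, hand laceration) are aimed at lifestyle and care-seeking behaviour.

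**4. Which measures are named for each outcome?**

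| Outcome | Section | Measures named |
|---|---|---|
| Primary composite | 9.7.3 | weighted rates, cumulative incidence, HR; RR and risk difference at 6, 12 and 18 months |
| AMI; heart failure hospitalisation | 9.7.4.1 | rates, cumulative incidence, HR |
| New-onset heart failure | 9.7.4.2 | rates, cumulative incidence, HR |
| UACR decline | 9.7.4.3 | rates, cumulative incidence; HR only if feasible |
| Hyperkalaemia | 9.7.4.4 | rates |
| All-cause mortality (exploratory) | 9.7.5.1 | Kaplan-Meier plots, HR |

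The UACR section makes its comparison conditional and gives the reason, which is the frequency of testing. The hyperkalaemia section gives no reason.

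**5. What could a residual potassium difference do?** This is an illustration only; none of its inputs is in the protocol. Let *d* be the difference in mean potassium that remains after weighting, and *k* the multiplier of the hyperkalaemia hazard per 0.5 mEq/L, with a log-linear effect. The apparent HR is then the true HR × k^(−d/0.5) if initiators have the lower potassium, and × k^(+d/0.5) if they have the higher. For a true HR of 1.5:

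| d (mEq/L) | k | factor, initiators lower | HR reads | factor, initiators higher | HR reads |
|---|---|---|---|---|---|
| 0.05 | 1.5 | 1.5^(−0.1) = 0.960 | 1.44 | 1.041 | 1.56 |
| 0.1 | 2 | 2^(−0.2) = 0.871 | 1.31 | 1.149 | 1.72 |
| 0.2 | 3 | 3^(−0.4) = 0.644 | 0.97 | 1.552 | 2.33 |
| 0.3 | 3 | 3^(−0.6) = 0.517 | 0.78 | 1.933 | 2.90 |

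The exclusion and the correlated covariates should make *d* smaller than any crude difference, but by an unknown amount. If *d* is zero there is no bias from this source.

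**The case against.** **The comparison is planned.** A reader might infer from 9.7.4.4 that no hyperkalaemia contrast will be estimated at all. The documents do not support that. The objective in 8.2 is comparative, the abstract plans weighted hazard ratios and mentions time-specific risk ratios and risk differences without tying them to one outcome, and 9.7.6 plans a hyperkalaemia hazard ratio in at least one subgroup. Section 9.7.4.4 also points to 9.7.3, which contains every measure. This objection largely stands: what remains is an inconsistency to reconcile. The cross-reference does not settle it, because 9.7.4.1 and 9.7.4.2 use the same reference and still name the HR.

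**Hyperkalaemia is not uniquely short-changed.** UACR decline has no firm HR, and neither 9.7.4.1 nor 9.7.4.2 names risk differences. That is correct. Asking for a risk difference here rests on the purpose of a safety outcome, not on parity with the other secondary outcomes.

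**Potassium is partly controlled.** High recorded values are excluded, several proxies are listed, and 9.7.2 applies the weights to all analyses. This also stands. The gap is possible residual confounding, not an unadjusted outcome.

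**The direction is not known.** A reader might infer that prescribers steer away from higher potassium, so that the analysis would mask an excess risk. The protocol does not establish this. Section 9.9 raises the possibility that users have more advanced disease, which would raise their outcome rate, the opposite direction.

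**Potassium may often be missing.** Laboratory results supplement the claims data (9.4), eligibility requires no test, and 9.10.2 allows missingness indicators when missingness is minimal. This is a real constraint on the remedy. However, 9.3.1 already uses an unknown category for UACR, so the device is not foreign to the protocol.

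**Conclusion.** Two limited points hold. First, the covariate list claims to cover hyperkalaemia risk factors but omits the baseline potassium value, and neither the exclusion, the proxies nor the planned diagnostics fully replaces it. The resulting confounding is possible at or below 5.0 mEq/L and in unmeasured patients. Its size and direction cannot be derived from the protocol, and the illustrated range depends wholly on assumed inputs. The documents do not support a claim that harm will be understated.

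Second, 9.7.4.4 is inconsistent with 8.2, the abstract and 9.7.6, because it names group-specific rates and no overall between-group measure. This is a fault of wording, but it concerns the only outcome labelled as safety. Both points should be corrected before the analysis starts.

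**What to change.** - **9.3.4 and 9.7.2:** add the most recent baseline serum potassium value to the propensity score model for the hyperkalaemia outcome, with a not-measured category as already done for UACR. State how this fits the minimal-missingness condition in 9.10.2. Report the proportion measured and the weighted balance of the value by group.
- **Sensitivity analysis:** repeat the hyperkalaemia comparison in patients with a measured baseline value.
- **9.7.4.4:** name the weighted cumulative incidence, the overall HR, and the RR and risk difference at 6, 12 and 18 months, each with a 95% CI obtained as in 9.7.3.

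**Cost:** a few sentences and a little more programming. The value is already needed for eligibility and for the dosage description, so no new data are required. The main downside is that potassium may be missing for many patients: the category would then adjust only partly, and the measured subset could be smaller and less representative.
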